4.3. Treatment Compliance

For each subject, the treatment compliance rate is estimated as follows

Compliance rate (%) = $100 * \text{actual treatment duration} / \text{intended treatment duration}$

More specifically, the actual treatment duration will be calculated by minimum of [Day 45 date, last dose date, and the first primary efficacy outcome date] - first dose date + 1 - dose interruption days up to Day 45. The intended treatment duration will be calculated by minimum of [Day 45 date, death date, and the first primary efficacy outcome date] - first dose date + 1 - dose interruption days up to Day 45 due to the reasons specified in protocol 10.2.1 (for example, hospitalization, bleeding, and other AEs).

Compliance rate will be summarized by treatment group.

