7. TREATMENT COMPLIANCE

The IWRS will keep track of study drug dispensed to the subjects. Subjects will return empty study drug containers and unused study drug at the Day 21 visit when a new supply of study drug is to be received. The last dose of study drug should be taken on Day 45. **Regardless of the day on which the Day 45 Visit occurs, no study drug may be taken after Day 45.** Subjects will also return empty study drug containers and unused study drug at the Day 45 (+4d) visit.

Study drug accountability will be performed at the Day 21 and Day 45 visits. Subjects should report any unintentional interruption or missed doses to the study-site personnel at each visit. It is understood that subjects may occasionally miss a dose or that a subject may be placed on temporary interruption (see Section 10.2.1, Temporary Interruption of Study Treatment).

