9.1.3. Double-Blind Treatment Phase

Day 1/Day of Randomization

If the subject meets all of the inclusion and none of the exclusion criteria, he or she is eligible to be randomly assigned to receive rivaroxaban or placebo at the Day 1 visit.

Randomization should occur on the day the subject leaves the hospital; randomization will also be permitted the day after the subject leaves the hospital. Randomization may occur at the hospital, clinic or other discharge destination.

At the randomization visit, before randomization occurs, site staff must review the visit schedule and the importance of completing the study with both the subject and any family members present. Randomization should not occur if the subject:

- does not have transportation to study visits
- does not believe they will have sufficient support to comply with the protocol
- is being discharged to a destination other than home and acceptability of study participation has not been confirmed with the accepting physician
- post-discharge anticoagulation or thromboprophylaxis is planned

Also, before randomization occurs, site staff should review eligibility criteria, including concomitant medications administered during the index hospitalization and planned at discharge. Particular attention should be paid to ensure that acceptable types and doses of thromboprophylaxis were used during the index hospitalization, and that prohibited medications were not administered and are not planned.

After randomization, the first dose of study drug should be administered as soon as possible and no later than the day after the subject leaves the hospital. The time of the first dose should be recorded as accurately as possible. The first dose also should not be delayed to allow administration under supervision. The first dose does not need to be delayed because of the recent administration of LMWH or UFH. The administration date and time of the first dose of study drug will be recorded in the source document and eCRF. The subject will be instructed to take study drug daily through Day 45. **Regardless of the day on which the Day 45 Visit occurs, no study drug may be taken after Day 45.**

Also, at the randomization visit, the importance of reporting signs and symptoms associated with bleeding, DVT and PE will be stressed. Subjects and family members, as appropriate, will be counseled and given educational material on the signs and symptoms associated with DVT, PE and bleeding.

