10.2.3. Permanent Discontinuation of Study Treatment

If a subject must be permanently discontinued from study drug before the end of the double-blind treatment phase, this will not result in automatic withdrawal of the subject from the study, and the subject should continue to be followed for efficacy and safety outcomes (for details see Section 3.1).

A subject should be permanently discontinued from study drug if:

- The investigator believes that for safety reasons (ie, adverse event) it is in the best interest of the subject to stop study drug.
- The subject develops any condition which requires anticoagulation or thromboprophylaxis extending beyond the treatment phase of the study (eg, atrial fibrillation, VTE).
- The subject becomes pregnant.
- The subject has a fall in CrCl to below 20 mL/min or 2 consecutive measurements less than 30 mL/min at least 1 week apart (as calculated by Cockcroft-Gault formula, see Section 9.1.2) during the study.
- The subject requires hemofiltration or dialysis on a permanent basis
- The subject requests to discontinue study drug permanently
- The subject has a hemorrhagic stroke, or intracranial bleeding

If the subject permanently discontinues study drug before Day 45, he/she should be instructed to complete an unscheduled visit and the remaining scheduled visits, including the Day 7 and Day 21 visits (if not yet completed), and Day 45 (+4d) and Day 75 (\pm 5d) visits (Section 9.1.3). The Day 45 visit should be a clinic visit; the Day 75 visit may be a telephone visit.

The eCRF is to be completed to identify the reason for permanent discontinuation of study drug. The investigator will provide a narrative to describe any adverse events that occur up to the Day 75 (\pm 5d) visit. The appropriate adverse event or serious adverse event sections of the eCRF

are to be completed. If study drug is terminated for a serious adverse event, expedited reporting (within 24 hours) is also required as outlined in Section 12.3.2, Serious Adverse Events.

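### The SAP 4.3 compliance formula subtracts interruption days up to Day 45 from durations that may end earlier, so some subjects get negative, above-100% or undefined rates

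*SAP*

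**What the plan says.** SAP 4.3 computes, for each subject, 100 times the actual treatment duration divided by the intended treatment duration.

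- **Actual duration:** the minimum of the Day 45 date, "last dose date, and the first primary efficacy outcome date] - first dose date + 1 - dose interruption days up to Day 45", whatever the reason for the interruption.
- **Intended duration:** the window is "minimum of [Day 45 date, death date, and the first primary efficacy outcome date] - first dose date + 1", less "dose interruption days up to Day 45 due to the reasons specified in protocol 10.2.1".

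The SAP does not define a dose interruption day. It does not say how an interruption that is never restarted is to be counted. The resulting rate is summarized by treatment group and used for nothing else.

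The protocol supplies the surrounding rules.

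- Section 9.1.3: "The subject will be instructed to take study drug daily through Day 45".
- Section 10.2.1 lists reasons for temporary interruption. Section 10.2.3 opens a separate list with "A subject should be permanently discontinued from study drug if".
- Section 9.2.2 lets study drug be restarted after a suspected efficacy event when no condition for permanent discontinuation is present.
- Section 7: "Study drug accountability will be performed at the Day 21 and Day 45 visits". The same section has subjects report missed doses at each visit, and Section 6 sends interruptions to the eCRF.

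**The concern.** Each duration is a window with its own closing date: last dose, first primary event, death or Day 45. The days removed for interruption are counted to one fixed date, Day 45. Whenever a window closes before Day 45 and interruption days fall after it closes, the formula subtracts days that were never in the window. In the numerator, an interruption that follows the last dose is removed twice: once because the window stops at the last dose, and again as interruption days.

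Subjects take the drug themselves for 45 days, so a reader of the ITT hazard ratio, especially a null one, will look at the compliance table. That table should not contain impossible values, or plausible ones that are wrong.

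Two neighbouring features also draw attention. Stops under Section 10.2.3 do not shorten the intended duration, and the tablet accountability is not used.

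**Working it through.** SAP 4.3 states no numerical result to reproduce, so the check applies its formula literally to illustrative courses. In all of them the first dose is on Day 1. The event, stop and interruption days are assumptions.

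**Ordinary courses behave.**
- Full course: 45/45 = 100%.
- Ten-day interruption for a 10.2.1 reason, then restart: 35/35 = 100%.
- Five days off for another reason: 40/45 = 88.9%.
- Drug stopped at a primary event on Day 10: 10/10 = 100%.

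**Courses with interruption days outside a window.** In courses 2 to 5 drug is restarted and the last dose is on Day 45. The last column counts interruption days only inside each term's own window.

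| Course | Actual | Intended | As written | Confined to window |
|---|---|---|---|---|
| 1. Last dose Day 10; 10.2.1 interruption logged as temporary Days 11–45, no restart | 10 − 35 = −25 | 45 − 35 = 10 | −250% | 10/10 = 100% |
| 2. Primary event Day 10; interruption Days 11–30, not a 10.2.1 reason | 10 − 20 = −10 | 10 | −100% | 10/10 = 100% |
| 3. Primary event Day 20; 6 own missed days before it; 10.2.1 interruption Days 21–35 | 20 − 21 = −1 | 20 − 15 = 5 | −20% | 14/20 = 70% |
| 4. Primary event Day 10; 3 own missed days before it; 10.2.1 interruption Days 11–22 | 10 − 15 = −5 | 10 − 12 = −2 | 250% | 7/10 = 70% |
| 5. Primary event Day 10; 10.2.1 interruption Days 11–20 | 10 − 10 = 0 | 10 − 10 = 0 | undefined | 10/10 = 100% |
| 6. Last dose Day 15; 10.2.1 interruption Days 16–20; death Day 20 | 15 − 5 = 10 | 20 − 5 = 15 | 66.7% | 15/15 = 100% |

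**Course 1 in general.** If the last dose is on Day k and the excused interruption stays open to Day 45, then actual = k − (45 − k) = 2k − 45, intended = k, and the rate is (2k − 45)/k. At k = 10 this is −250%, at k = 22 it is −1/22 = −4.5%, at k = 30 it is 15/30 = 50%, and at k = 40 it is 35/40 = 87.5%. Confined to the window, the rate is k/k = 100% throughout. The later versions look plausible, so a range check would miss them.

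**Effect on a group mean.** The documents do not give the frequency of such courses, so a range of 0.1% to 1% of subjects is assumed. With every case at k = 10 (350 points too low), the mean falls by 0.35 to 3.5 points. With every case at k = 30 (50 points too low), it falls by 0.05 to 0.5 points.

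**The two neighbouring features.**
- A 10.2.3 stop on Day 5, 10, 20, 30 or 40 scores 11.1%, 22.2%, 44.4%, 66.7% or 88.9%. If 1% to 5% of a group stop this way on Day 22 (assumed), each loses 100 × (1 − 22/45) = 51.1 points, and the mean falls by 0.5 to 2.6 points.
- With 2, 5 or 9 missed tablets of 45 that are never logged, the formula gives 100%. A tablet count gives 95.6%, 88.9% or 80.0%.

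**The case against.** The strongest reply is that the impossible values need uncommon sequences. An interruption with no later dose can be regarded as a permanent discontinuation, for which the eCRF takes a reason. Course 1 is then 10/45 = 22.2%, not −250%. The other route, restart after a primary event, is narrow, because Section 10.2.3 names VTE as an example of a condition that leads to permanent discontinuation. If every post-event day is excused and none was missed before the event, the two errors can also cancel: an event on Day 10 with a 10.2.1 interruption on Days 11–30 gives −10/−10 = 100%.

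The point about frequency stands. It does not rescue the wording. Section 10.2.1 sets conditions for restart, such as resolution of a bleed or two platelet values at least a week apart, that can easily run past Day 45. Because interruption days are undefined, the course 1 subject can be scored −250%, 22.2% or 100% depending on logging and programming.

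A reader might infer three stronger things that the documents do not support.

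- **That the adherence result as a whole is unreliable.** Ordinary courses compute correctly. Reasons for stopping and time to last dose (SAP 4.2) and exposure (SAP 4.4) are reported separately.
- **That the handling of 10.2.3 stops biases the comparison against rivaroxaban.** No arm difference in such stops is given. As a scale, major bleeding in the earlier rivaroxaban trial in medically ill patients was 1.1% versus 0.4%. If that whole 0.7-point excess became permanent stops on Day 1, the arm mean would move by 0.7 × 44/45, about 0.7 points. Not excusing these stops also fits a measure of planned treatment received and matches the closing dates of the completer definition in SAP 4.2. Ending the intended duration at the stop would score a Day 5 stop as 100% and hide lost exposure.
- **That missed tablets go uncounted.** Missed doses are reported at every visit and interruptions are recorded in the eCRF. The gap is limited to doses not logged.

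**Conclusion.** Wrong as written (window mismatch), minor. Followed literally, SAP 4.3 gives negative, above-100% or undefined rates for a minority of subjects, and plausible but too-low rates for some others. The −250% figure assumes an excused interruption from Day 11 that is logged as temporary to Day 45 and never restarted. The negative and above-100% values after a primary event assume a restart. How many subjects would be affected cannot be derived from the documents.

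The rate is descriptive. It enters no test, has no cut-off in the per-protocol definition (SAP 2.3) and does not touch the ITT primary analysis, so the primary conclusion is unaffected. The treatment of 10.2.3 stops is a defensible choice to be made visible, not an error. Tablet counts are a useful supplement, not a necessary replacement.

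**What to change.** 1. In SAP 4.3, in both numerator and denominator, subtract only interruption days that fall on or before the end date used in that same term. This turns all six courses above into valid values.
2. In the same sentence, define a dose interruption day and say how an interruption never restarted by Day 45 is classed. Say also that the rate is not calculated when a primary event precedes the first dose: event Day 1 and first dose Day 2 give 1 − 2 + 1 = 0 in both terms, which item 1 does not cure.
3. As a supplement, report tablet-count compliance by arm, (dispensed − returned) over intended dosing days, from the Day 21 and Day 45 accountability.
4. Report permanent stops required by Section 10.2.3 as a separate line by arm, with the subject's own request shown apart, and leave their compliance score unchanged.

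The cost is a few lines of SAP text and a little programming on data already collected. The one added decision is a convention for bottles that are not returned.

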4.4. Extent of Exposure

The number of subjects who take at least one dose of study drug will be provided for each treatment group.

Subject level duration of treatment exposure is defined as the duration between the first dose date and last dose date. Note that temporary study drug interruptions are included in this definition.

Duration of treatment exposure will be summarized by treatment.

4.5. Protocol Deviations

Protocol deviations will be summarized by treatment group. The categories of protocol deviations may include, but are not limited to, the following:

- Did not meet the inclusion or exclusion criteria
- Received wrong treatment or incorrect dose
- Did not discontinue study drug permanently according to the protocol
- Had been taking prohibited concomitant therapies as specified in the protocol

4.6. Prior and Concomitant Medications

Medication will be coded using the Anatomical Therapeutic Chemical (ATC) dictionary. The prevalence of medication use by ATC term will be summarized by treatment group and by study phase (prior to the first dose of study drug, during the study drug therapy period, and after last dose of study drug [post-treatment]). A medication that starts prior to the first dose of study drug is considered as a prior medication. A medication with a use period overlapping with the period between the first and last dose of study drug is considered as a concomitant medication. A medication that starts after the day of the last dose of study drug is considered as a post-treatment medication. Note that a medication use can be categorized into multiple study phases if its use spans into more than one study phase. In such a case, the medication use will be included in more than one summary.

5. EFFICACY

Unless otherwise stated, interim and final efficacy analyses will be based on CEC adjudicated events.

5.1. Analysis Specifications

5.1.1. Level of Significance

Unless otherwise specified, all statistical tests will be interpreted at a 2-sided nominal significance level of 0.05 and all confidence intervals at a 2-sided level of 95%.

5.1.2. Data Handling Rules

If the date of an outcome event is missing or partially missing, the earliest logically possible date after randomization will be used as the event date. The date of an outcome event is defined as the maximum of randomization and the first day of month if only day is missing and is defined as the first day of the following month after randomization if day and month are missing.

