1.2. Trial Design

This is a multicenter, prospective, randomized, double-blind, placebo-controlled, event-driven study designed to evaluate rivaroxaban, compared with placebo, in the prevention of symptomatic VTE (lower extremity DVT and non-fatal PE) events and VTE-related deaths (death due to PE or death in which PE cannot be ruled out as the cause) for a period of 45 days post-hospital discharge. The first dose of study drug should be administered no later than the day after the subject leaves the hospital and as soon after randomization (Day 1) as possible. Subjects will be instructed to discontinue study drug after they take a dose on Day 45. The subject population comprises men and women age 40 and over who had been hospitalized for at least 3 and no more than 10 consecutive days prior to randomization for a specific acute medical illness and have other risk factors for VTE. Subjects who meet all of the inclusion and none of the exclusion criteria will be randomly assigned to receive rivaroxaban or placebo. Randomization should occur on the same day as or the day after the subject leaves the hospital, and may occur at the hospital, clinic, or other discharge destination. Subjects will be randomized by strata (by subjects with a CrCl ≥ 30 mL/min and < 50 mL/min versus subjects with CrCl ≥ 50 mL/min, and by country) by an interactive web response system (IWRS). After randomization, subjects will receive double-blind treatment with rivaroxaban 10 mg (7.5 mg for subjects with a CrCl ≥ 30 mL/min and < 50 mL/min) daily or matching placebo daily.

The targeted total number of primary efficacy outcome in this event-driven study is 161. It is estimated that a total of approximately 8,000 subjects will need to be randomized to either rivaroxaban or placebo in 1:1 ratio. This estimate is based on an estimated placebo incidence rate of the primary efficacy outcome of 2.5%. In the event that the actual observed blinded pooled event rate is lower than the assumed rate, more subjects may be enrolled to accumulate additional outcome events. Randomization in this study may be stopped at approximately 12,000 subjects for administrative considerations even if the targeted 161 events have not been observed by then. The total number of VTE-related death events may also be taken into account when deciding to stop randomization.

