An interim analysis for futility will be conducted when approximately 50% of subjects with an adjudicated primary efficacy outcome have been observed (about 50% of the expected total number of events based on the actual observed blinded pooled event rate even if this event rate is lower than the assumed rate).

Prior to randomization, all subjects must have received treatment during the index hospitalization with LMWH or UFH. The study consists of a screening phase, a 45-day double-blind treatment phase, and a 30-day follow-up. The total duration for a subject who completes the study after randomization is expected to be 75 days.

If the subject permanently discontinues treatment before Day 45, he/she should be instructed to complete an unscheduled visit and the remaining scheduled visits, including the Day 7 and Day 21 visits (if not yet completed) and the Day 45 (+4d) and Day 75 (± 5 d) visits

If a subject withdraws consent from the study or is lost to follow-up, his or her vital status and outcomes will be collected at the day 75 (± 5 d) visit either by telephone or in person, or if applicable, by a review of subject's medical or public records unless this contact is not allowed by local regulations.

For population PK analyses, based on the model performance and high variability of the PK parameters observed in the MAGELLaN study, at the Day 7 visit 2 blood samples (at pre-dose; 1-4 hours after study drug administration) and again at Day 21 visit (Visit 4) 2 blood samples (at 3 to 7 and 7 to 12 hours after study drug administration) will be collected for each subject for about 600 subjects (300 rivaroxaban subjects [200 subjects in the 10 mg QD group and 100 subjects in the 7.5 mg QD group] and 300 in the placebo group). The sparse blood samples for PK analyses will be collected in selected sites only.

An Executive Committee (EC), an Independent Data Monitoring Committee (IDMC) and a Clinical Event Committee (CEC) will be commissioned for this study.

The EC has overall responsibility for the design, conduct and reporting of the study. The EC will monitor overall safety during the study and will receive any recommendations from the IDMC regarding possible additional analyses or modifications to the study and decide whether to accept them. The EC will oversee the implementation of any modifications to the study.

[figure not shown]

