2.1. Definition of Trial Dates

Trial reference start date: the date of randomization of the subject.

Trial reference end date: the date of the last trial-related procedure for the subject and is defined as the maximum of the following dates:

- Dates of all study-related visits (including scheduled or unscheduled visits)
- Dates of all study-related procedures, findings and events, including, but not limited to, adverse events, concomitant medications, disposition, clinical laboratories, vital signs, death

First dose date: the date on which the first dose of study drug is taken by the subject. If missing or incomplete for a subject who takes study drug, the first dose date is set to the earliest logically possible date on or after randomization. More specifically, the first dose date is defined as the maximum of the randomization date and the first day of the month if only day is missing, and is defined as the randomization date if day and month are missing.

Last dose date: the date on which the last dose of study drug is taken by the subject. If missing or incomplete for a subject who takes study drug, the last dose date is in general set to the latest logically possible date on or after the first dose date.

To ensure consistency with other data of the trial, more specifically, the above date will be further

- capped by (that is, taking the minimum with) Day 45 date, death date, trial reference end date, and the upper bound of the logically possible range if partial date is available, and
- further bounded below by (that is, taking the maximum with) the (imputed) first dose date, any complete temporary drug stop and re-start date, or the lower bound of the logically possible range.

Upper bound of the logically possible range is defined as the last day of the month if only day is missing and is defined as the last day of the following month after randomization if day and month are missing. Lower bound of the logically possible range is defined the maximum of the randomization date and the first day of the month if only day is missing and is defined as the randomization date if day and month are missing.

Last outcome-evaluation date: the date of last study visit (clinic/phone) while the subject is alive during which the outcome status is ascertained.

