2.3. Analysis set and Analysis Phase

Each analysis involves the following 2 aspects: 1) analysis set, specifying the subjects to be included; and 2) analysis phase, specifying the time window within which data will be included.

Key analysis sets and analysis phases are defined below.

Analysis sets

- Intention-to-Treat (ITT) (as termed Full Analysis Set in the International Conference on Harmonisation [ICH] E9 guideline): This analysis set consists of all randomized subjects who have a signed valid informed consent.
- Per-Protocol (PP): This analysis set is a subset of the ITT analysis set.

Subjects with the key protocol deviations will be excluded from the PP analysis set. The categories and terms of the key protocol deviations will include the following:

- Did not meet the following inclusion or met the following exclusion criteria;
 - INT-2, INT-3, INT-4: subject with index hospitalization > 14 days, inclusion criteria 1, 2, 4, 6, exclusion criteria 10, 11, 14, 22, 24, 27
 - INT-6, INT-7: inclusion criteria 1.2, 2.2, 4.3, 6.1, exclusion criteria 10.2, 11.1, 14.1, 22.2, 24.2 without c
- Did not take any assigned study drug or took wrong study drug
- Did not discontinue study drug permanently according to the protocol (The subject becomes pregnant, develops any condition which requires permanent anticoagulation, has a fall in CrCl to below 20 mL/min during the study, or has a hemorrhagic stroke or intracranial bleeding)
- Had been taking prohibited concomitant therapies as specified in the protocol
 - INT-2: 2, 3,
 - INT-3, INT-4: 2, 3, 4, 6, 7, 8
 - INT-6, INT-7: 2.2, 3.2, 4.1, 7.1 without c and i

- Safety: This analysis set is a subset of the ITT analysis set, consisting of subjects who receive at least one dose of study drug.

Analysis phases

- Up-to-Day-45: This analysis phase includes all data from randomization to Day 45 (inclusive).

For time to event analyses, subjects who do not have events to be analyzed on or before Day 45 will be censored on Day 45 or the last outcome-evaluation date whichever occurs first.

- On-Treatment: This analysis phase includes all data from randomization to 2 days after the last dose of the study drug (inclusive).

For time to event analyses, subjects who do not have events to be analyzed during this phase will be censored on the last dose + 2 or the last outcome-evaluation date whichever occurs first.

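### With day and month missing, the SAP's outcome-date rule departs from its own earliest-date principle and can contradict the recorded year

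*SAP*

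**What the plan says.** SAP 5.1.2 (Data Handling Rules) covers outcome events whose date is wholly or partly missing. It first gives a principle: "the earliest logically possible date after randomization will be used as the event date". It then gives two operational branches.

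- Only the day missing: "The date of an outcome event is defined as the maximum of randomization and the first day of month if only day is missing".
- Day and month missing: the date "is defined as the first day of the following month after randomization if day and month are missing".

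The second branch does not mention the recorded year. Neither branch is limited by an earlier event-free visit, by death or by last contact.

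SAP 2.1 states nearly the same principle for the first dose: "the first dose date is set to the earliest logically possible date on or after randomization". There, the date "is defined as the randomization date if day and month are missing". For the last dose, SAP 2.1 also caps the imputed date by, among others, the death date and the trial reference end date.

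The primary analysis phase runs from randomization to Day 45 inclusive (SAP 2.3), and randomization is Day 1 (SAP 1.2). Follow-up goes further: "The total duration for a subject who completes the study after randomization is expected to be 75 days". Protocol 9.1.4 has suspected outcome events reviewed again at the Day 75 visit.

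**The concern.** A programmer cannot satisfy both the principle and the day-and-month branch, because they give different dates for the same record. The branch also discards information. If the year is known, it limits when the event can have happened, and near a year end it can settle whether the event lies inside Day 45.

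The rule supplies the event indicator and the event time for the primary Cox analysis (SAP 5.2.2), and so the count towards the 161-event target (SAP 1.4). Protocol section 11 leaves imputation rules for partial dates to the SAP, so SAP 5.1.2 is where the rule has to be right. Incomplete dates are most plausible for subjects who withdrew or were lost, whose outcomes may be obtained by telephone or from records (Protocol 10.3).

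**Working it through.** The plan gives no figure on this point to reproduce. The check applies the rule as written to every randomization date in 2016 (366 dates, chosen for illustration; 2014 to 2017 together give the same percentages to the precision quoted).

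**Gap from randomization.** Imputed date = first day of the month after randomization. It falls 1 to 31 days after randomization (mean 15.8), that is on Day 2 to Day 32. It never equals the randomization date. It equals the day after randomization only for month-end randomizations, 12 of 366 dates (3.3%). So even a strict reading of the word *after* in the principle does not rescue the branch. The day-only branch permits the randomization date itself, which suggests that a strict reading was not meant.

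**Recorded year.** With the year known, the earliest possible date is max(randomization date, 1 January of the recorded year).

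| Randomized | Recorded year | Rule as written | Earliest possible date |
|---|---|---|---|
| 10 Dec 2016 | 2016 | 1 Jan 2017 (Day 23) | 10 Dec 2016 (Day 1) |
| 20 Nov 2016 | 2017 | 1 Dec 2016 (Day 12) | 1 Jan 2017 (Day 43) |
| 25 Oct 2016 | 2017 | 1 Nov 2016 (Day 8) | 1 Jan 2017 (Day 69) |

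In all three rows the rule gives a year that the record contradicts. In the third it also reverses the Day 45 status.

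**How often, given day and month missing and year known.** Assume uniform randomization dates and event days 1 to 75, so 366 × 75 = 27,450 equally likely pairs. Let d be the study day of the next 1 January.

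- December randomizations (d = 2 to 32), event in the randomization year: the rule gives the next year. Pairs: 1 + 2 + … + 31 = 496.
- Randomizations from 19 October to 30 November (d = 75 down to 33), event in the next year: the rule stays in the randomization year. Pairs: 1 + 2 + … + 43 = 946.
- Wrong year: (496 + 946) / 27,450 = 1,442 / 27,450 = 5.3%.
- Year alone proves the event was after Day 45 (d = 46 to 75), yet the rule puts it inside: 1 + 2 + … + 30 = 465 pairs; 465 / 27,450 = 1.7%.

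If follow-up runs to Day 80, the late edge of the Day 75 visit window, the two shares are 5.7% and 2.2%. Among events within Day 45 only, 3.6% get the wrong year and none changes window status.

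**What the corrected date changes.** There are 366 × 30 = 10,980 pairs on Days 46 to 75. The rule as written places all of them inside Day 45, because its latest imputed day is Day 32. The year-aware date moves 465 back outside (4.2%). The other 95.8% stay inside, because the earliest possible date is still early.

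**Missing cap.** The imputed day can be as late as Day 32 and SAP 5.1.2 states no cap. A subject who died or was last seen before then could be given an event date after death or last contact.

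**The case against.** The strongest reply concerns size, and most of it stands. Analyses use adjudicated events (SAP section 5). DVT and PE generally need imaging, echocardiography or autopsy (Protocol Attachment 1). Hospital and imaging records are requested (Attachment 2), and symptoms are asked about at Days 7, 21, 45 and 75. An adjudicated event with neither day nor month known should be rare.

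The comparison with the first-dose rule is also of limited weight. The first dose is meant to follow randomization closely, so the randomization date is a natural default there and less so for an outcome. Finally, programming instructions sit in a separate document (SAP section 1) that is not available here, and it may resolve the conflict.

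A reader might infer more than the documents support, in three ways.

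- *Every undated event is misclassified.* This is not so. An event truly within Day 45 keeps the right window status; only its day may be wrong. Under the uniform assumption that is 45/75 = 60% of cases.
- *The faulty clause is what draws late events into the primary window.* It does so for every Day 46 to 75 event with day and month missing, but the year-aware date would still draw in 95.8% of them. In the day-only branch about 49% of Day 46 to 75 events are drawn in, and that branch follows the stated principle. These shares come mainly from a prespecified, inclusive choice of the earliest date, not from the contradiction.
- *The treatment comparison is biased.* The rule does not depend on treatment arm, and adjudication is blinded (Protocol 3.3.3). Nothing in the documents shows a differential effect.

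None of this removes the contradiction or the disregard of the recorded year.

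**Conclusion.** SAP 5.1.2 is wrong as written for events with day and month missing: the branch contradicts the principle it is meant to implement, and it can override a recorded year. Given such an event with a known year, about 5% would get a contradictory year. About 1.7% would be counted as primary events although the record proves they came after Day 45. Both shares assume uniform randomization dates and event days over Days 1 to 75.

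The documents do not say how many events this touches. The number is probably very small, so the effect on the hazard ratio cannot be calculated and is likely to be slight. Severity: minor, a wording correction to a rule that feeds the primary endpoint.

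**What to change.** Rewrite the day-and-month branch of SAP 5.1.2 so that the event date is the later of the randomization date and 1 January of the recorded year. Bound it below by the last visit at which the subject was recorded event-free, and above by the death date and last contact. SAP 2.1 already applies caps of the latter kind to the last dose. State what applies if the year is missing as well.

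Add one sensitivity analysis of the primary outcome that excludes events whose possible date range spans Day 45. This shows how far the result depends on the inclusive choice, which the new date leaves largely in place. The effect of the event-free-visit bound cannot be estimated from the documents.

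The cost is a short change of wording and minor extra programming for the bounds and the repeated analysis. It should be made before unblinding.
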